- b. The number and frequency of nCLE procedure-related AE/SAE from the start of the procedure until end of 12-month follow-up
- 8. To assess the reproducibility of nCLE criteria to the reference standard. Three nCLE characteristics for the detection of malignancy were identified during Wijmans et al. study [10]:
 - a. Dark enlarged pleomorphic cells;
 - b. Dark cell clusters consist of overlapping cell structures ('dark clumps') and
 - c. Continuous movement of the cells in one direction ('directional streaming').
- 9. To create an nCLE image atlas for malignant characteristics in PPNs.

3. Study Design

This is a randomized, controlled, interventional, comparative prospective multi-center study. In total, a maximum of 118 consecutive patients with a (suspected) PPN who are referred for a diagnostic bronchoscopic (Robotic-guided TBNA) procedure will be considered for enrollment. The estimated duration of the study is 24 months. Patients will be consecutively recruited and randomly assigned to undergo Robotic-guided TBNA (n=59) or Robotic-nCLE-guided TBNA (n=59).

Only patients in the nCLE arm will receive intravenously administered fluorescein before the start of the Robotic procedure. During the nCLE procedure, an 18G needle enters the targeted tissue, followed by an nCLE AQ-Flex™ 19N Confocal Miniprobe™ (Mauna Kea Technologies, France) through the biopsy needle, to obtain real-time imaging. nCLE imaging will be performed in the PPNs with a total estimated time for research measurements of 10 minutes. nCLE imaging will be performed for each sequential TBNA pass/sampling within the lung nodule lesion and each TBNA path cytopathological result will be correlated with the nCLE sequence acquired for that TBNA pass. TBNA sampling will end when sufficient diagnostic material will be found with ROSE (as assessed by the cytopathologist) or when the physician performing the procedure judges that the number of samplings/passes is adequate. ROSE will be performed by a cytopathologist.

4. Study Population

Population (base)

Patients with a PPN referred for diagnostic bronchoscopic/endosonographic workup tissue sampling based on standard (PET-) CT imaging

Inclusion criteria

To be eligible to participate in this study, a study subject must meet all of the following criteria:

- ≥ 21 years of age
- Suspected PPN
- Nodule size in CT between 8 mm and 30 mm (largest dimension)

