- Ability to understand and willingness to sign a written informed consent and HIPAA consent document

Exclusion criteria

- Inability or non-willingness to provide informed consent
- Failure to comply with the study protocol
- Patients with known allergy for fluorescein or risk factors for an allergic reaction
- Use of beta-blocker within 24 hours before the start of the bronchoscopic procedure
- Possibly pregnant, pregnant or breastfeeding women
- Patients with hemodynamic instability
- Patients with refractory hypoxemia
- Patients with a therapeutic anticoagulant that cannot be held for an appropriate interval before the procedure
- Patients who are unable to tolerate general anesthesia according to the anesthesiologist
- Patient undergoing chemotherapy

Intra-operative Exclusion/Stopping Criteria:

- The lesions are unable to be localized/confirmed by bronchoscopy
- The procedure will be terminated if the patient develops a significant procedural complication as determined by the treating physician
- The procedure will be terminated if the patient develops hemodynamic instability as determined by the treating physician

Sample size calculation

A bronchoscopic TBNA (Robotic-guided TBNA or Robotic-nCLE-guided TBNA) will be regarded as successful when histological confirmation of the diagnosis is achieved and matches the final diagnosis. If additional TBNA passes or tests, e.g., further bronchoscopies, surgery, etc., are needed to establish the diagnosis, the TBNA pass will be regarded as non-diagnostic.

We will calculate TBNA diagnostic yield for the cumulative number of passes until five cumulated passes for both the Robotic-guided TBNA and Robotic-nCLE-guided TBNA arms. It is anticipated that sequential passes at a target site will result in stepwise yield increments to a plateau. Every needle pass at a location will be reported separately and entered into a database to provide yields after each sequential pass.

Proportional data will be compared using a Chi-squared test of contingency tables or Fisher's exact test on 2x2 contingency tables in the case of very small counts (<5).

First- and cumulative-pass diagnostic yields:

Diagnostic yields for the different cumulative passes are defined as follows:

1. First-pass diagnostic yield is calculated as the proportion of patients for which first-pass TBNA during the bronchoscopic procedure yielded a definitive diagnosis out of the total number of patients that have received a diagnostic procedure.

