Microscopic, real-time image sequences are recorded, and cellular structures are visualized as desired. If at any time the ~3 mm Confocal Miniprobe™ protrusion interferes with the TBNA procedure, the Confocal Miniprobe™ can be pulled back into the needle by unlocking the purple screw to change directions, and then advanced again and locked. As long as the white screw remains locked, the Confocal Miniprobe™ cannot be advanced further than ~ 3mm beyond the distal needle tip and will not be damaged.

Retrieval of the probe

When the physician has completed imaging tissue with the Confocal Miniprobe™, it can be removed from the needle by unlocking the purple screw and extracting the probe. The locking device is a single-use device and is discarded after the procedure.

9. After imaging, extract the Confocal Miniprobe™ and locking device assembly from the needle	10. Remove the locking device from the Confocal Miniprobe™ and discard it
-----------------------------------------------------------------------------------------------	---------------------------------------------------------------------------

Further biopsies may then be performed with a 20 g needle, forceps, or brush per standard of care at the discretion of the bronchoscopist. After the biopsies, a bronchial-alveolar lavage may be performed per standard of care at the discretion of the bronchoscopist. Endobronchial ultrasound (EBUS) with lymph node biopsies will also be performed when indicated as part of the standard of care.

If a second lesion requires a biopsy, the bronchoscope will be withdrawn, and the chest will be imaged by fluoroscopy or chest ultrasound to rule out pneumothorax per standard of care. The bronchoscope can then be re-inserted, followed by navigation to the second lesion. However, only one lesion will be imaged with nCLE per patient.

After the Cellvizio® procedure

After removal of the Confocal Miniprobe™, the tissue can be routinely aspirated per the standard TBNA procedure and analyzed for chemistry, cytology, and/or tumor markers. nCLE imaging will not interfere with tissue / fluid specimen collection during the remainder of the conventional TBNA procedure.

Steps of standard - and study (in bold) procedures:

1. Patients will be sedated following standard procedure.
2. **(research-purposes) After starting the procedure, we will administer 2.5 ml of fluorescein 10% intravenously to visualize the CLE images only in the patients in the Robotic-nCLE-guided TBNA arm).**

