During the nCLE procedure the bronchoscopist will judge quality of the image, lung lesion detection, and presence of malignancy. The bronchoscopist will be trained in nCLE image evaluation.

Validation session

The trained raters will evaluate nCLE videos of all 59 patients as a randomized data-set and be blinded to the patient history and cytologic/pathologic diagnosis. Videos used for the training session will be excluded. The results of the nCLE video reviews will be compared to the corresponding cytological or histopathological results. The first session will be performed to assess the nCLE characteristics, image quality and confidence and will be used to calculate the inter-observer agreement (IOA) between the raters for detecting malignancies based on nCLE videos. The second session will be performed by the same group of raters, after a 2-week wash-out period, using the same set nCLE videos in a different order to assess the intra-observer reliability (IOR).

Pathological examination

During bronchoscopy, the sites suspected of malignancy will be evaluated with nCLE. In the case of positive tumor cytology (nodes/tumor) or histology (tumor), this will be the reference standard for the nCLE images. In the case of tumor negative cytology or histology, additional surgical/pathological staging or clinical/radiological follow-up will be available.

Cytological aspiration (standard procedure)

During the bronchoscopic procedure, the cytological aspirations will be evaluated on-site by a cytopathologist (ROSE). The appearance of cancer cells will be reported and shown on screen to the endoscopist. Definitive diagnosis of the sample follows after re-evaluation by a staff member of the pathological department. No additional samples will be taken for the research protocol, nor will the research protocol interfere with the pathological diagnostic protocol.

Histological evaluation

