Suppose a patient suspected of lung cancer has a negative result of the bronchoscopic procedure. In that case, a surgical procedure (mediastinoscopy or lobectomy/pneumectomy with lymph node dissection) could follow to obtain tissue. This surgical procedure will be performed regardless of the result of nCLE imaging. If a surgical procedure is indicated, we will collect the histological images to compare with nCLE imaging. This study will not interfere with the standard cytology or the standard histology process. Digital copies of the cytological and histological slides of the measured nodules will be obtained and compared with the frames of the nCLE sequences.

Final Diagnosis or Definitive Diagnosis

For this 12-month analysis, pathology results of Robotic-aided biopsy samples that will be diagnostic of a non-malignant condition or indeterminate will be referred to as negative for malignancy or negative for brevity. Follow-up will be conducted to determine the final diagnosis (malignant or non-malignant). All cases will be followed according to the practitioner's judgment and standard of care testing (e.g., surgical tissue biopsy, repeat Robotic, CT-guided transthoracic needle biopsy or aspiration (TTNA), serial CT imaging, and lung health visits). Cases with subsequent diagnostic tests confirming a non-malignant diagnosis or without lesion progression on radiographic follow-up will be considered true-negative at 12 months, consistent with prior Robotic studies. If the follow-up diagnostics reveal malignancy or lesion growth on repeat imaging with appropriate follow-up diagnostic testing, this will be considered a false-negative. The following will also be regarded as false-negative: death due to lung cancer within 12 months; treatment without a confirmed diagnosis; and new diagnosis of cancer in the lung from any site (including non-index lesions or lymph nodes diagnosed as malignant by linear bronchoscopy during or after the index procedure).

Twelve-month diagnostic yield will be calculated per subject as the rate of true-positives (for malignancy) plus true negatives (for malignancy) of all subjects with attempted lung lesion biopsies.

Adverse Events

Definitions

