Based on investigator self-assessment, the proportion of cases in which the operator can successfully navigate to the lung target with Robotic guidance and Robotic-nCLE guidance will also be recorded and compared for both arms. Using a statistical test (Student T-test), the navigation success will be compared between arms (Robotic-guided TBNA and Robotic-nCLE-guided TBNA).

Navigation time

Total time that the locatable guide/ nCLE Confocal MiniprobeTM is used in the subject during the Robotic-guided TBNA or Robotic-nCLE-guided TBNA procedure. The navigation time medians and standard deviations will be calculated for both arms. Using a statistical test (Student T-test), they will be compared between arms (Robotic-guided TBNA and Robotic-nCLE-guided TBNA).

First- and cumulative-pass diagnostic yields and performance calculations

First-pass diagnostic yield was defined above (see section Sample size calculation for the definition). Two first-pass diagnostic yields will be calculated one for the Robotic-nCLE-guided TBNA arm and a second one for the Robotic-guided TBNA arm. 95% confidence intervals will be calculated, and the p-value to compare diagnostic yield values between the two arms. Sequential cumulative pass diagnostic yields will also be calculated for each arm.

The diagnostic performance of the sequential cumulative ROSE passes and the sequential cumulative nCLE passes for the Robotic-nCLE-guided TBNA arm and of ROSE only for the Robotic guided TBNA will also be assessed at the end of a follow-up period according to their sensitivities, specificities, positive predictive value (PPV), and negative predictive value (NPV). The sensitivity test will measure the ability of sequential cumulative ROSE passes or sequential cumulative nCLE passes to characterize malignant nodule (true positive rate) correctly. In contrast, the specificity test will measure the ability for sequential cumulative ROSE passes or sequential cumulative nCLE passes to correctly characterize benign nodule (true negative rate) using the final/definitive diagnosis as the reference.

Where a = true positive, b = false positive, c = false negative, and d = true negative:

- Sensitivity: Probability that sequential cumulative ROSE passes will be positive when malignancy is present (true positive rate): $= a/(a + c)$

- Specificity: Probability that a sequential cumulative ROSE passes will be negative when malignancy is not present (true negative rate): $= d/(b + d)$

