- Accuracy: Probability that a Robotic-guided biopsy gives correct prediction among the total number of cases examined: $= (a + d)/(a + b + c + d)$

Patient diagnostic and management analysis:

Intermediate and final diagnosis and management recommendation proportion differences for the two patient populations (Robotic-guided TBNA arm and Robotic-nCLE-guided TBNA arm) will be compared using a chi-square test. Intermediate and final diagnosis and management recommendation proportions will also be compared for the two patient populations. Differences between Robotic-guided TBNA and Robotic-nCLE-guided TBNA arms regarding the specific diagnostic and management categories will be compared using McNemar's test both at the intermediate diagnosis and the final diagnosis stage.

Feasibility statistical analysis:

The feasibility of needle-based lung cancer diagnosis will be assessed by investigating the following items:

- Assessing nCLE-image quality
- Assessing the feasibility of the integrated needle/Cellvizio® I.V.E Confocal Miniprobe™.

The imaging feasibility yield for the Robotic-nCLE-guided TBNA procedure is defined as the proportion of patients in whom procedure will yield at least good nCLE image quality out of the total number of patients that will receive that procedure.

The mechanical feasibility yield for the Robotic-nCLE-guided TBNA procedure is defined as the proportion of patients for whom Robotic-nCLE-guided TBNA procedure will be possible mechanically (meaning that the nCLE probe will be guided to the nodule successfully) out of the total number of patients that will receive that procedure.

Safety:

The safety will be assessed by carefully monitoring adverse events related to both procedures. Serious adverse event rates will be calculated by dividing the number of events for each procedure divided by the total number of procedures for each arm.

Reproducibility:

To assess the reproducibility of bronchoscopy guided nCLE:

- Estimating the reproducibility of nCLE criteria will be evaluated by calculating the inter-observer agreement of nCLE criteria between 3 readers (Fleiss Kappa).

In Wijmans et al. [10], three nCLE characteristics for the detection of malignancy were identified in different subtypes of lung tumors and metastatic lymph nodes:

- 1) dark enlarged pleomorphic cells;
- 2) dark cell clusters consisting of overlapping cell structures ('dark clumps'); and

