- 3) the continuous movement of a part of the cells in one direction ('directional streaming')

These criteria will be evaluated qualitatively.

New nCLE characteristics in malignant and benign lung lesions could also be identified during this study. An imaging atlas of nCLE images will also be built for the different tumor types on in-vivo characteristics. The department of pathology will be strongly involved in this project.

nCLE-video images will be reviewed and diagnosed retrospectively, independently, and blindly by investigators, expert readers, and pathologists.

The diagnostic yield will be tested to give the likelihood that nCLE will provide the information needed to establish a diagnosis.

Correlation analysis will also be performed between:

- nCLE imaging results and digital images of cytological or histopathological results
- nCLE imaging results in different tumor types.

8. End Points

Primary endpoint: The definitive diagnosis will serve as the reference standard for the calculation of study endpoints. The study pathologists will not be aware of nCLE results. The primary endpoint of this study will be the first-pass diagnostic yield, as defined in the section "Sample size calculation", i.e. and is calculated as the proportion of patients for which first-pass TBNA during the bronchoscopic procedure yielded a definitive diagnosis out of the total number of patients that have received a diagnostic procedure

Secondary endpoint: The secondary outcome of this study will be the per-patient diagnostic yield, calculated as the proportion of patients in whom the bronchoscopic procedure yielded a definitive diagnosis out of the total number of patients that have received a diagnostic procedure.

Third endpoint: The third endpoint for patient management will be assessing the clinical impact of nCLE by determining the proportion of patients with a correct change in definitive diagnosis and the associated change in management plan with nCLE.

First-pass diagnostic yield:

The study is designed to enroll 118 patients who will be randomly assigned 1:1 to Robotic-guided TBNA alone or Robotic-nCLE-guided TBNA for a statistical power of 80% with a 2-sided significance level of 0.05 to detect an increase of the primary study endpoint (per pass TBNA diagnostic yield) of at least 20%, from 70% to 90%, between the Robotic-guided TBNA and the Robotic-nCLE-guided TBNA.

Per patient diagnostic yield (cumulative pass diagnostic yield) and performance:

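### Randomised patients with no needle pass most naturally fall out of the primary first-pass yield, on a decision taken by an operator who knows the arm

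*Combined protocol and SAP*

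**What the plan says.** Section 4, Intra-operative Exclusion/Stopping Criteria, opens with "The lesions are unable to be localized/confirmed by bronchoscopy". The other two criteria end the procedure for a significant complication or for hemodynamic instability.

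The primary first-pass yield is the share of patients with a definitive diagnosis from the first TBNA pass, "out of the total number of patients that have received a diagnostic procedure" (Section 4, Sample size calculation; repeated in Section 8, Primary endpoint). The background text before the objectives and the per-patient yield in Section 7 use very similar denominators. The background text identifies the bronchoscopic procedure with Robotic-guided TBNA or Robotic-nCLE-guided TBNA.

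The sample size section also has a scoring rule: a TBNA pass counts as non-diagnostic if further passes or tests are needed to reach the diagnosis. That rule covers a pass that was made.

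On timing, Section 3 says "Only patients in the nCLE arm will receive intravenously administered fluorescein before the start of the Robotic procedure". In Section 5, step 2 of the procedure list gives fluorescein "to visualize the CLE images only in the patients in the Robotic-nCLE-guided TBNA arm", and the target is localised only later, at step 5.

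No available text names an all-randomised, intention-to-treat or per-protocol set, or says how a randomised patient with no needle pass is counted. Figure 3, which shows the steps in each arm, and some removed pages could not be read.

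**The concern.** If the procedure received is TBNA, a patient whose lesion is never localised, or whose procedure is stopped before the first needle pass, has not received it and leaves the denominator. Each such patient is a randomised patient without a first-pass diagnosis, so removal raises that arm's yield.

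The removal happens after randomisation and rests on a judgement about localisation or confirmation, made by an operator who already knows whether fluorescein was given. Equal loss does no harm to the comparison. Unequal loss biases it, in whichever direction the imbalance runs. Because removal is implied and not stated, the set could also be settled after the first-pass results are known.

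**Working it through.** **1. The plan's own figure.** Inputs from Section 4: 70% v 90%, 80% power, two-sided 0.05, 1:1 allocation. With unpooled variance,

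n = (1.960 + 0.842)² × [0.70×0.30 + 0.90×0.10] / 0.20² = 7.849 × 0.30 / 0.04 = 58.87, so 59 per arm.

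The stated size reproduces. Exact power of the uncorrected chi-square test at 59 per arm is 80.5%. Neither figure allows for excluded patients.

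**2. Bias and error if patients without a pass are removed.** Assumptions: 59 randomised per arm; true yield 70% of all randomised patients in both arms; each patient independently unlocalised with probability q, always without a diagnosis. Yield among those remaining is 0.70/(1−q). For example, at q = 5% it is 0.70/0.95 = 73.7%, which is +3.7 points. Error rates come from exact binomial enumeration with the uncorrected chi-square test at two-sided 0.05; the plan's Fisher fallback for counts below 5 is not applied.

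| Loss, nCLE v control | Bias (points) | False nCLE win | False control win | Total error |
|---|---|---|---|---|
| 0% v 0% | 0 | 2.6% | 2.6% | 5.2% |
| 5% v 5% | 0 | 2.5% | 2.5% | 5.1% |
| 10% v 10% | 0 | 2.5% | 2.5% | 5.1% |
| 2% v 0% | +1.4 | 3.8% | 1.7% | 5.5% |
| 5% v 0% | +3.7 | 6.5% | 0.9% | 7.3% |
| 10% v 5% | +4.1 | 7.2% | 0.7% | 7.9% |
| 10% v 0% (extreme illustration) | +7.8 | 15.3% | 0.2% | 15.5% |

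Reversed rates give the mirror image. At 59 per arm, 2% is about one patient (59 × 0.02 = 1.2) and 5% about three (59 × 0.05 = 2.95).

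**3. One data set, two denominators (invented counts).** Control 41 diagnostic of 59; nCLE 49 diagnostic with 5 patients unlocalised.
- Received-procedure set: 41/59 (69.5%) v 49/54 (90.7%), chi-square p = 0.005.
- All randomised: 41/59 v 49/59 (83.1%), p = 0.083.

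If 3 control patients had also been unlocalised, the received-procedure comparison is 41/56 v 49/54, p = 0.017, against the same p = 0.083 for all randomised.

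**4. Power at 59 per arm.** The plan does not say which set the 70% and 90% describe.
- If they describe all randomised patients, an all-randomised analysis keeps the 80.5%.
- If they describe sampled patients only, keeping unlocalised patients as non-diagnostic multiplies both rates by (1−q):

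| q, equal in both arms | Removed: power | Kept: yields | Kept: power |
|---|---|---|---|
| 2% | 79% | 68.6% v 88.2% | 76% |
| 5% | 78% | 66.5% v 85.5% | 70% |
| 10% | 75% | 63.0% v 81.0% | 60% |

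**The case against.** Several counter-arguments have force.

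- **A denominator and a scoring rule exist.** The received-procedure denominator is written repeatedly and consistently, and a first pass that was made and failed is already non-diagnostic. This stands. The gap is confined to patients with no first pass.
- **Removal is not stated.** The heading pairs exclusion with stopping, and the other two criteria only end the procedure. The list could be no more than procedural stopping rules. This stands as a possible reading, but the word exclusion together with a received-TBNA denominator makes removal the more natural one.
- **Other sections count differently.** Mechanical feasibility keeps unreached nodules in ("meaning that the nCLE probe will be guided to the nodule successfully) out of the total number of patients that will receive that procedure"), Navigation success reports "the proportion of cases in which the operator can successfully navigate to the lung target with Robotic guidance", and the validation session expects videos from everyone ("The trained raters will evaluate nCLE videos of all 59 patients as a randomized data-set"). The twelve-month yield is taken "of all subjects with attempted lung lesion biopsies", which may leave out a patient with no attempted biopsy. A reader might infer that the plan contradicts itself on the primary denominator. It does not: each passage governs a different measure, and none settles the primary one.
- **The bias is hypothetical.** Localisation precedes probe imaging in both arms, no rate is given, and equal loss does no harm. This stands. A reader might infer that the rule favours nCLE; the documents do not show which arm, if either, would lose more.
- **Needle yield after localisation is a legitimate target,** because nCLE acts after localisation. It is defensible if specified in advance, but as the primary set it depends on a post-randomisation judgement made with the arm known. It fits better as a supportive analysis.

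**Conclusion.** The point holds in a limited form. As written, the plan most naturally removes randomised patients with no needle pass from the primary comparison, through a decision made with the arm known. It neither states that removal nor names an all-randomised set, subject to the material that could not be read.

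The size depends wholly on assumed rates. It is nil with equal loss, small with a one-patient imbalance (total error 5.5%), and worth preventing at about three patients' difference (total error 7.3% to 7.9%). The 10% v 0% case shows the extreme and is not a forecast.

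This should not be read as a claim that 59 per arm is wrong. The figure reproduces, and the stated 80% power stands for an all-randomised analysis if the 70% and 90% describe all randomised patients. It is a cheap improvement that should be made before the data are analysed.

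**What to change.** 1. Define the primary analysis set as all randomised patients, in their assigned arm.
2. Score first-pass yield as non-diagnostic for a patient with no first pass, whether the lesion was not localised or the procedure stopped before it. A patient stopped later keeps the first-pass result already obtained.
3. Leave the clinical stopping criteria unchanged, but state that meeting one does not remove the patient from the analysis.
4. Report non-localised and stopped patients by arm.
5. Keep an explicitly defined received-procedure set as a supportive analysis.
6. State which set the 70% and 90% describe. If all randomised patients, the 80% power stands. If sampled patients only, restate power at 59 per arm as about 76%, 70% or 60% at an assumed 2%, 5% or 10% unlocalised.

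**Cost.** Wording only. Ability to navigate to the lesion is already collected (Section 6, Procedural assessments) and compared by arm (Section 7, Navigation success). Yields will be slightly lower, and the primary estimand will include navigation failure; needle yield after localisation stays available in the supportive analysis. If the planning rates describe sampled patients only, the plan must report power below 80%.
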